6.2. Key Definitions

For the purposes of this study, the term “study drug” or “treatment” refers to BPN14770 or placebo.

The study day is the day relative to the date of first dose of study drug. If the assessment date is on or after the date of first dose of study drug, the study day is calculated as date of assessment - date of first dose of study drug + 1 (and thus the day of first dose is designated as Study Day 1). If the assessment date is prior to the date of first dose of study drug, the study day is calculated as date of assessment - date of first dose of study drug (and thus the day prior to first dose is designated as Study Day -1).

Unless otherwise specified, baseline is the last non-missing measurement before the first dose of the study drug, which is expected to be the baseline visit at Day 1, or screening if the Day 1 data are not available.

The change from baseline will be calculated for each Post-baseline assessment as:

This document is confidential.

- Change from Baseline = Post-baseline value – Baseline value.

6.3. Missing Data

For the primary efficacy determination, observed cases data will be utilized.

A supportive analyses will be performed for the primary efficacy endpoint to account for data missing at random (MAR) and for data missing not at random (MNAR). MNAR data are often due subjects discontinuing due to lack of efficacy or to due treatment-emergent AE. This sensitivity analysis will include the use of multiple imputation (MI). Multiple imputation provides a useful strategy for analyzing data sets with missing values. Instead of filling in a single value for each missing value, Rubin's ([Rubin 1987](#)) multiple imputation strategy replaces each missing value with a set of plausible values that represent the uncertainty about the correct value to impute. This analysis is described in the Primary efficacy endpoint section ([Section 8.1.1](#)).

6.4. Visit Windows

The visit windows are specified in the Schedule of Assessment in [Section 3.7](#). The visits recorded in database will be used for the analyses, and there is no plan to re-assign visits based on actual visit dates, except the Early Termination (ET) visit. For ET visit, the next scheduled visit closest to the termination date will be assigned for the efficacy analysis specified in [Section 8](#).

6.5. Pooling of Centers

Thirty eight (38) sites enrolled subjects into the study, with nearly 75% having enrolled < 10 subjects. As such, sites will be pooled based geographical location (based in US time zones: Eastern, Central/Mountain, Pacific) into pooled final site designations of at least 30 subjects per site.

6.6. Subgroups

Subgroup analysis of the primary efficacy endpoint will be performed for the following subgroups:

- Presence or absence of the ApoE4 allele
- By gender (male and female)
- Ethnicity (Hispanic vs non-Hispanic)
- MMSE (dichotomized as the baseline median across the pooled treatment groups)

Tabulation of the incidence of TEAEs will also be presented for those subgroups.

6.7. Data listings

Data listings will be presented for all data collected. The derived Study Day will be presented along with the date in these data listings. Specifically for TEAEs and medications, the Study Start Day and Study Stop Day will be included. Listings will be sorted by subject number, and then study visit or study day, accordingly.

This document is confidential.

7. Demographic, Other Baseline Characteristics and Medication

7.1. Subject Disposition and Withdrawals

Subject disposition will be summarized for the Screened Population.

For subject study status, the number and percentage of subjects for each one of the following categories will be presented by treatment groups and overall.

- Screened subjects (Total only)
- Screen failure subjects (Total Only)
- Randomized Population
- Safety Population
- Modified Intent-to-Treat Population
- Per Protocol Population
- Completers Population
- Subjects who completed the study
- Subjects who discontinued the study prematurely by primary reason

For all categories of subjects (except for the screened subjects and screen failures), percentages will be calculated using the number of randomized subjects as the denominator, unless otherwise specified.

Subject disposition and analysis populations data will be listed with clear indication of which populations in which each subject has been included.

7.2. Demographic and Other Baseline Characteristics

The following demographic and baseline variables will be summarized using the Safety Population and the mITT population, by treatment group and overall:

- Age (years)
- Age categorized (as <65, >=65 to <75, and >=75)
- Gender
- Race
- Ethnicity
- Body mass index (BMI) (kg/m²) at baseline
- BMI categorized (dichotomized at <30 kg/m² vs >= 30 kg/m²)
- APOE4 test results (presence / absence of the allele)
- Pre-treatment MMSE

This document is confidential.

- MMSE categorized as ≥ 26 , 23 to 25, < 23
- RBANS DMI
- RBANS DMI by median overall (pooled across all treatment groups) $<$ median vs \geq median

Modified Hachinski Ischemia Score (MHIS), smoking history, alcohol consumption, drug use, serology, and pregnancy test results will be collected and listed but not summarized.

7.3. Medical/Surgical History

Medical/surgical history as recorded at screening will be summarized using the Safety Population by treatment group using the number and percentage of subjects reporting each system organ class (SOC) and preferred term (PT). Medical/surgical history will be sorted by descending overall total by SOC and PT using the Medical Dictionary for Regulatory Activities (MedDRA) coding dictionary version 22.0 in the summary table.

Medical/surgical history data will be listed and sorted by treatment group, site, subject number, onset date, SOC, and PT.

7.4. Medication

All concomitant medications taken 14-days prior to the first dose of study drug (Day 1) and during the study through the Week 14 Follow-up Visit should be recorded with indication, daily dose, and start and stop dates of administration.

- Prior medications are those medications taken and stopped before the start of study drug dosing.
- Concomitant medications are medications that are ongoing at or taken on or after the start of study drug dosing.
- New-onset concomitant medications are defined as those medications starting between the first dose of double-blind study medication and 1 day (24 hours) after the start of the last dose of double-blind study medication. Medications with no start time but starting on the day of double-blind study medication will be assumed to be new-onset.

Prior, concomitant, and new-onset medications will be summarized by the number and percentage of subjects taking a particular medication. All the medications will be listed.

A summary of concomitant medications taken during the course of the study will be presented in tabular form using Anatomical Therapeutic Chemical (ATC) classification level 2 and PT via the World Health Organization Drug (WHODrug) Global B3 Mar 2019. The medications will be summarized using the Safety Population by treatment group and sorted alphabetically by ATC level 2 class and PT. If a subject has taken a medication more than once, the subject will be counted only once in the same ATC class or PT.

Medications with incomplete end dates will be considered a concomitant medication if:

- Day and month are missing and the year is equal to or after the year of the first dose date;
- Day is missing and the year is after the year of the first dose;

This document is confidential.

- Day is missing and the year is equal to the year of the first dose date and the month is equal to or after the month of the first dose date;
- Year is missing; or
- Entire date is missing.

The medication data will be listed, and sorted by treatment group, site, subject number, prior and concomitant status, onset date, ATC level, and PT.

This document is confidential.

8. Efficacy

8.1. Primary Efficacy Endpoint and Analysis – RBANS DMI

The Repeatable Battery for the Assessment of Neurological Status (RBANS) [Randolph 1998] is a brief, individually administered test measuring attention, language, visuospatial/constructional abilities, and immediate and delayed memory. It consists of 12 subtests, which yield five Index scores and a Total Scale score.

Total scores are calculated by adding up the scores for each of the 12 individual subtests and ranges between 0 and 311, where a low score indicates greater impairment. The range of possible scores for the RBANS DMI is 40 to 160.

The primary efficacy outcome measure is the change from baseline to Week 13 in the delayed memory index of the RBANS [Repeatable Battery for the Assessment of Neurological Status - Delayed Memory Index (RBANS DMI)]. Observed cases data (with no imputation for missing values) will be used for primary efficacy analysis.

The original RBANS DMI score and change from baseline will be summarized by treatment group at each time point.

The primary method of analysis will be an MMRM with restricted maximum likelihood estimation, an unstructured covariance matrix, and the Kenward-Roger approximation for denominator degrees of freedom. The model will include fixed effects for treatment, visit (time), the treatment-by-time interaction, ApoE4, pooled study site, the baseline RBANS DMI score as covariate, and a random effect for subject. [Similar models will be defined for the other continuous secondary efficacy endpoints.] Primary inferences will be drawn from treatment differences in the LSmean changes from baseline derived from the MMRM models at Week 13. As additional supportive information, treatment differences for Weeks 1, 4, and 8 will also be derived using the MMRM model. Least Squares Means for each visit and the SE of the LSMeans will be displayed graphically.

In an MMRM model, missing data are not explicitly imputed. Instead, all available postbaseline assessments up to endpoint for the subjects in the mITT population are utilized and, via modelling of the within subject correlation structure, endpoint treatment differences which are adjusted to take account of missing data are derived. The estimation of treatment differences using the MMRM model is based upon an assumption that the missing data follows a missing-at-random mechanism (i.e., the missingness of the observations may be dependent on the observed outcomes or covariates, but not on unobserved outcomes). For this primary analysis, no imputation of the missing values will be made or required and the data used in the analysis will be the actual observed responses at each visit.

Example SAS code:

```
Proc Mixed data=indat ;  
  class trtp SITEGR1 ApoE4 avisitn subjid;  
  model chg= base SITEGR1 ApoE4 trtp avisitn trtp*avisitn /ddfm=kr;  
  Random intercept / subject=subjid;  
  repeated avisitn / type=un subject=subjid;  
  lsmeans trtp*avisitn /cl diff ;  
run;
```

This document is confidential.

In the unlikely circumstance that there are convergence problems with the MMRM analysis, this will be explored. For example, the SCORING=4 option could be used in the MIXED statement, which makes SAS use Fisher scoring for the first 4 iterations. If the convergence problem cannot be resolved, the unstructured covariance matrix will be replaced by the AR(1) covariance structure in combination with a random subject effect.

8.1.1. Sensitivity Analysis using Multiple Imputation (MI) Approach for the Primary Efficacy Endpoint of RBANS DMI

A listing of the number of subjects with each unique missing pattern for the RBANS DMI will be presented. This will be generated using PROC MI in SAS (see example, Table 3). These data will be examined in order to determine if there was any general difference in the pattern of missing data between the treatment groups, as well as to explore the assumption of missingness at random.

Table 3 Examples of Patterns of Missingness

Pattern	Treatment Group	Number (%) of Subjects	Baseline	Week 1	Week 2	Week 4	Week 8	Week 13
1	25 mg	xx (xx.x%)	X	X	X	X	X	X
	10 mg	xx (xx.x%)	X	X	X	X	X	X
	Placebo	xx (xx.x%)	X	X	X	X	X	X
2	25 mg	xx (xx.x%)	X	X	X	X	X	.
	10 mg	xx (xx.x%)	X	X	X	X	X	.
	Placebo	xx (xx.x%)	X	X	X	X	X	.
Etc.								

For the primary endpoint (RBANS-DMI), 100 imputed datasets will be created, with data imputation for missing values due to missingness at random as well as due to discontinuation due to AE or due to lack of efficacy. The 100 imputed datasets were analyzed using an analysis of covariance (ANCOVA) model with contrasts to test the primary efficacy endpoint. The model used treatment as the main effect and stratification factor ApoE4, pooled study site and baseline RBANS-DMI as covariates. Data from all three treatment groups were included in the same ANCOVA model for purposes of the testing procedures.

The 100 resulting treatment effect parameters and standard errors (SEs) from these ANCOVA were presented individually and then combined to provide a distribution of parameters (and SEs) upon which the primary hypothesis of treatment effect was determined. The results of the analyses were presented in summary tables with standard summary statistics as well as least squares (LS) means, active versus placebo LS mean differences (treated group – placebo), SEs, confidence intervals, and paired-comparison p-values. The mean RBANS-DMI values and standard errors of the mean (SEM) for each treatment group were also presented graphically. This analysis was referred to as the multiple imputation analysis.

Imputation Methodology:

For subjects with arbitrary missing data patterns (missing at random [MAR]), here meant to represent RBANS-DMI scores that were missing for reasons other than the subject discontinuing (and specifically, ‘intermediate time points’, eg, a subject has a valid non-missing Week 4 RBANS-DMI, but no Week 8, the

This document is confidential.

Week 8 score is considered MAR), a Markov chain Monte Carlo method (Schafer 1997) that assumed multivariate normality to impute all such MAR missing values was used to create preliminary imputed (resulting) data sets that have strictly monotone missing patterns. A monotone missing pattern implies that all observations after a certain time point are missing, but that there are no intermediate missing values. This pattern occurs when missing values are usually caused by subject discontinuation.

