3.2. Brief Description

This is a Phase 2, randomized, double-blind, placebo-controlled, 3-arm, parallel-design study to evaluate the effects of BPN14770 in approximately 255 subjects with a clinical diagnosis of early stage AD. The study will consist of a Screening period of 28 days or less. The Screening period will be followed by a 13-week double-blind treatment period, and a final follow-up visit for safety one week after treatment is concluded.

Randomization will be stratified based on presence or absence of an ApoE4 allele in the subject's genetic profile. Within each stratum, subjects will be randomized in a blinded, balanced fashion to receive either BPN14770 10mg bid, BPN14770 25 mg bid, or matching placebo. A target of 80 evaluable subjects per group (240 total) is planned (see the sample size determination in [Section 3.4](#)). Approximately 85 subjects per group will be enrolled (255 total) in order to account for potential dropouts. Subjects will have a total of eight clinic visits: Screening; Baseline (Day 1); Weeks 1, 2, 4, 8, 13, and the final Follow-up Visit. The screening visit will consist of consenting the subject, obtaining a medical history, full physical exam, height, weight, BMI, ECG, serology and drug testing, chemistry, hematology, urinalysis, ApoE4 testing, pregnancy testing, and cognitive assessments. If the subject fully qualifies for the study, randomization will occur at the Baseline visit following verification of continued eligibility, at which time the subject will receive study medication.

Cognitive testing will occur at each visit, Week 1 through Week 13, but not at the final Follow-up Visit (note, not all cognitive assessments are performed at each visit). Safety assessments will also be performed at each visit, to include adverse event monitoring, vital signs, ECG, and chemistry and hematology. Urinalysis will also be performed at Screening and Baseline and Weeks 1, 4 and 13. Lipid testing will be performed at Baseline and Week 13. Risk of suicidality will be assessed at Screening, Baseline and Weeks 1, 4, and 13.

Pharmacokinetic sampling will be performed at the clinic visits at Weeks 1, 4, 8 and 13.

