3.4. Determination of Sample Size

The BPN14770-CNS-201 study will enroll 255 subjects (85 per treatment arm), in anticipation of evaluating at least 240 subjects (80 per treatment). The Primary Efficacy Outcome measure will be change from baseline at Week 13 for the Repeatable Battery for the Assessment of Neurological Status - Delayed Memory Index (RBANS DMI).

The normalized mean of the RBANS DMI is 100, with an SD of 15, and the test-retest reliability is 0.80 with no practice effects using alternate versions of the test [Randolph 1998]. RBANS DMI was used in a recent natural history study of Mild Cognitive Impairment (MCI) due to probable AD [Karantzoulis 2013]. In the large amnesic MCI sample (81 subjects), the mean was 73.4 with a SD of 16.5 in a normal distribution. Performance of healthy, age-matched controls was a mean of 101.4 with a SD of 14.4 (81 subjects) yielding estimates of the standard deviation for the DMI from 14.4-16.5. Therefore, the power analysis is based on the assumption that the standard deviation of the response variable is 16.

The power of the proposed study is driven by the assumed difference between BPN14770 25mg (higher dose) and placebo. Based on randomization of 80 subjects per group into the parallel-design study, the probability is 80 percent that the study will detect a treatment difference at a two-sided 0.05 significance level, if the true difference between BPN14770 25 mg and placebo is 7.15 units. Using the standardized mean difference (SMD) to estimate effect size [Faraone 2008], a change of 7.15 units on the DMI score is an effect size of 0.45.

Table 1 provides sample size estimates for 80 percent and 90 percent probability that the study will detect a treatment difference at a two-sided 0.05 significance level assuming the standard deviation of the DMI is 16.

Table 1 Clinical Sample Size (1:1 Active + Placebo) Based on Effect Size (Change From Baseline) And Desired Power

	Number of Subjects Per Group Based on Desired Effect Size (SMD)					
Standardized Mean Difference (SMD)	0.3	0.35	0.4	0.45	0.5	0.75
RBANS DMI change (M1-M2)	4.8	5.6	6.4	7.2	8	12
Number of Subjects (Power 0.8)	176	130	100	79	64	29
Number of Subjects (Power 0.9)	235	173	133	105	86	39

For comparison, a donepezil study reported by Seltzer et al., 2004, randomized a total of 153 subjects (2:1 active vs placebo) and reported treatment benefit at a significance level of 0.03 after 12 weeks of

This document is confidential.

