3.5. Treatment Assignment & Blinding

In this randomized, double-blind, placebo controlled, 3-arm, parallel group study, 255 subjects will be assigned to receive one of three treatments via balanced randomization (1:1:1). Randomization will occur separately within each ApoE4 stratum (presence/absence of ApoE4 isoform) to ensure similar numbers of ApoE4 positive subjects are present in each treatment group. The three treatments are:

- A. BPN14770 10mg, twice-daily
- B. BPN14770 25mg, twice-daily
- C. Matched placebo, twice daily

A randomization schedule will be generated by a statistician unassociated with the study execution prior to the start of the study. Subjects will be randomized on Day 1 and receive their bottle of medication that same day.

This is a randomized, double-blind study, meaning that neither site staff nor subject will know what the subject is receiving. Sponsor staff are also blinded to treatment assignments.

Randomization codes will be provided to the Investigator or designee for use in case of an emergency code break requirement. Confirmation of receipt of the randomization code will be required by the Sponsor. The PI or designee will be responsible for maintaining the blind, consistent with protocol design, throughout the study, except in the case of an emergency code break.

The Investigator will be required to notify the Sponsor in the event of any breaking of the blind for any reason. Blinding is not to be broken during the study unless considered necessary by the Investigator for emergency situations for reasons of subject safety. The Investigator should contact the Medical Monitor before breaking the blind. When the blind is broken, the reason must be fully documented.

Except in the event of an emergency code break for an individual subject, the subjects, Investigator, and all other study personnel involved with subject assessments will remain blinded to the actual treatment assignments of the subjects. The Investigator will be ultimately responsible for ensuring that the integrity of the blind is maintained throughout the study.

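### The primary MMRM shares one baseline DMI slope across five visits; a baseline-by-visit term would usually sharpen the Week 13 comparison slightly, at negligible cost

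*SAP*

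**What the plan says.** SAP 8.1 gives the terms of the primary MMRM: "The model will include fixed effects for treatment, visit (time), the treatment-by-time interaction, ApoE4, pooled study site, the baseline RBANS DMI score as covariate". Treatment-by-time is the only interaction with visit. The example PROC MIXED code agrees with the text: "model chg= base SITEGR1 ApoE4 trtp avisitn trtp*avisitn /ddfm=kr". The covariance is unstructured, and primary inference is at Week 13.

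The schedule (protocol 16.1, SAP 3.7) collects RBANS at Weeks 1, 2, 4, 8 and 13, so five post-baseline visits share one baseline slope. The ANCOVA in protocol 11.4 likewise has baseline as a single covariate and week-by-treatment as its only interaction. Neither document gives a reason for holding the slope constant.

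The multiple-imputation sensitivity analysis (SAP 8.1.1) is different. It fits an ANCOVA to Week 13 change alone, so its baseline slope is specific to Week 13.

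**The concern.** The model lets the treatment effect and the covariance vary freely by visit but not the baseline slope. If scores taken soon after baseline correlate with it more strongly than scores at Week 13, the slope of change on baseline is steeper at Week 13 than earlier. The fitted common slope is then a compromise weighted across visits. Part of the baseline-related variation at Week 13 stays in the error of the one contrast that carries the primary conclusion.

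Three things could be at stake: precision at Week 13, the way the model predicts missing Week 13 values, and the comparison of the primary result with its sensitivity analysis. The last two analyses differ in mean model as well as in missing-data assumption, so a gap between them could not be put down to missingness alone.

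**Working it through.** **1. The plan's own figure.** SAP 3.4 says "the probability is 80 percent that the study will detect a treatment difference at a two-sided 0.05 significance level"; the target is an advantage of 7.15 units for the higher dose. It adds that "the power analysis is based on the assumption that the standard deviation of the response variable is 16". The normal approximation gives n = 2 × (1.960 + 0.842)² × 16² / 7.15² = 78.6, so 79 per arm. Noncentral-t power at 80 per arm is 80.2%. All twelve Table 1 entries reproduce. The calculation is an unadjusted two-sample one: it uses neither baseline nor the repeated measures, so the proposed term does not alter it.

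**2. Inputs for the slope question.**
- From the documents: five visits, 80 per arm, SD 16 (taken here as the score SD at each visit), reliability 0.80, an entry cap on DMI of 85, and a scale floor of 40.
- Assumed: baseline correlation ρ(t) of 0.80 or 0.85 at Week 1, decaying exponentially in weeks to 0.60-0.70 at Week 13, with the same decay between post-baseline visits.
- Baseline SD: the plan's MCI distribution (mean 73.4, SD 16.5), taken as normal and truncated to 40-85, has SD 10.9. This assumes that the cap applies to the baseline score used as covariate. SD 16 is shown as the untruncated case.

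**3. Formulas.**
- Slope of change on baseline at visit t: β(t) = ρ(t) − 1.
- Common slope under an unstructured residual covariance S: b = (1ᵀS⁻¹β) / (1ᵀS⁻¹1).
- Week 13 residual variance with its own slope: v = 16² × (1 − ρ(13)²).
- Inflation from the common slope: (β(13) − b)² × Var(baseline) / v. Truncating baseline changes Var(baseline) only.
- Power: Φ(7.15 / √(2V/80) − 1.96), with V = v, or v plus the slope-mismatch term.

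Example, 0.80 to 0.65: β(13) = −0.35, b = −0.239, v = 256 × (1 − 0.4225) = 147.84. The mismatch is 0.111, so inflation is about 0.111² × 256 / 147.84 = 2.1% at SD 16, and 0.111² × 10.9² / 147.84 = 1.0% at SD 10.9.

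| Week 1 to Week 13 correlation | β(13) | b | Inflation, SD 10.9 | Inflation, SD 16 | Power at SD 16, common → own slope |
|---|---|---|---|---|---|
| 0.80 to 0.70 | −0.30 | −0.228 | 0.5% | 1.0% | 97.6% → 97.7% |
| 0.80 to 0.65 | −0.35 | −0.239 | 1.0% | 2.1% | 95.7% → 96.1% |
| 0.80 to 0.60 | −0.40 | −0.250 | 1.6% | 3.5% | 93.5% → 94.2% |
| 0.85 to 0.70 | −0.30 | −0.184 | 1.2% | 2.6% | 97.4% → 97.7% |
| 0.85 to 0.65 | −0.35 | −0.193 | 2.0% | 4.3% | 95.4% → 96.1% |
| 0.85 to 0.60 | −0.40 | −0.201 | 2.9% | 6.2% | 92.9% → 94.2% |

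The largest power change is 1.3 points, in the last row. At SD 10.9 that row gives 93.6% → 94.2%.

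**4. Other residual structures.** With the correlation falling linearly by visit from 0.80, SD 16, and compound-symmetric, autoregressive or independent residuals, inflation is about 0.6-0.8% for a fall to 0.70 and about 2-3.5% for a fall to 0.60. The order of size is the same.

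**5. Cost when the slopes are equal.** In a simulation of 3 × 80 complete cases (1,500 replicates, flat correlation 0.80), the Week 13 SE was 1.5226 with a common slope and 1.5241 with visit-specific slopes. Since (1.5241/1.5226)² = 1.002, variance rises by about 0.2%. Contrasts were unbiased within simulation error under both models, here and with falling correlations.

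**6. Dropout.** A second simulation used a true effect of zero, correlation 0.80 to 0.65 and monotone dropout at assumed rates.
- Dropout unrelated to baseline: the two models differ by 0.01 units.
- Active arm losing 20% of low-baseline and 5% of high-baseline subjects, other arms 6%: they differ by 0.13 units.
- Stress case, 30% dropout among low-baseline subjects on active and among high-baseline subjects on placebo: −0.36 against +0.15 (SE 0.10 each). The gap of 0.51 is 7% of 7.15.

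**The case against.** The best reply is that a common slope is a legitimate prespecified choice, consistent with protocol 11.4, and that the harm rests on a decay in correlation that the documents never state. That stands as far as it goes: the point is conditional. It is also true that the entry cap makes the smaller range the relevant one, and that baseline adjustment at these correlations already puts power for 7.15 units well above the planned 80%, so no decision turns on the term.

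On missing data, the unstructured covariance uses each dropout's observed post-baseline scores, so prediction does not rest on the baseline slope alone. Planned attrition is low: "Approximately 85 subjects per group will be enrolled (255 total) in order to account for potential dropouts", or 5/85 = 5.9%. The effect is small unless dropout is heavy, depends on baseline and differs by arm.

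What does not stand is that this is merely a matter of taste. The term relaxes a constraint for which the SAP offers no reason, it costs almost nothing, and the SAP's own sensitivity ANCOVA already works without that constraint.

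**Conclusion.** The point holds as a cheap improvement. Under the assumed fall in correlation, the common slope inflates Week 13 variance by about 0.5-3% at a baseline SD near 11, equivalent to roughly 0.4 to 2.3 of 80 subjects per arm, and by about 1-6% at SD 16. Power changes by about one percentage point or less, apart from 1.3 points in the most extreme case at SD 16.

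A reader might infer three stronger things that the documents do not support:
- That the term recovers precision for free. The gain depends on slopes the documents do not give. It is zero if the slopes are equal, and variance is then about 0.2% larger.
- That the primary comparison is biased. With complete data the randomised contrast is not. An effect through baseline-dependent, arm-differential dropout is possible, but small under mild dropout.
- That the study is underpowered as a result. The sample size does not use the baseline covariate and is unaffected.

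**What to change.** Before unblinding, add `base*avisitn` to the primary MMRM in both the text and the example code of SAP 8.1. Add it also to the secondary MMRMs that have a baseline covariate and more than one post-baseline visit: RBANS total and the other indices, MMSE, and ADCS-ADL. It does not apply to CDR-SB or m-ADCOMS, which are assessed after baseline at Week 13 only, or to CGI-I, which has no baseline. Record the added term in SAP section 12.

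The cost is four extra slope parameters for the five-visit endpoints and one for ADCS-ADL (Weeks 8 and 13), negligible with about 240 subjects. The primary model then has a Week 13-specific baseline slope, as the MI sensitivity ANCOVA already has, so a difference between the two analyses is easier to read as a missing-data effect.

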10.2 Screening (Day -28 to Day -1)

The study will consist of a Screening period of 28 days or less, unless additional time is required for washout of concomitant medications.

Each potential study participant will have the following assessments completed by the Investigator or designee up to 28 days prior to the first dose of study medication:

- Obtain informed consent;
- Obtain medical/surgical history;
- Obtain demographics and social history (tobacco, alcohol, and/or drug use);
- Obtain prior/concomitant medication use;
- Obtain vital signs;
- Obtain height and weight;
- Conduct full physical exam;
- Conduct single ECG;
- Serology (HbsAg, HCV)
- Serum pregnancy (females of childbearing potential , even if using birth control)
- Draw blood samples for Chemistry and Hematology (fasting or nonfasting);
- Collect urine for safety urinalysis;
- ApoE4 testing, if not in medical history;

- Conduct C-SSRS assessment;
- Conduct RBANS, MMSE, CDR and MHIS evaluations
- Evaluate inclusion and exclusion criteria.

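### RBANS DMI is measured twice before randomization but the primary models adjust for the Day 1 score only; adding the Screening score could cut Week 13 residual variance by 0% to about 16%, at almost no cost

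*SAP*

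**What the plan says.** **Two pre-treatment scores.** Protocol 10.2 lists, at Screening, "Conduct RBANS, MMSE, CDR and MHIS evaluations". Protocol 8.12 and 10.3 repeat RBANS on Day 1 before randomization, and both schedules of assessments agree. A DMI cut-off is an entry criterion: 85 or less in Protocol 6.2, strictly below 85 in SAP 3.3. A Screening DMI should therefore exist for essentially every randomized subject.

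**One is used.** SAP 6.2 states that "baseline is the last non-missing measurement before the first dose of the study drug". It expects this to be Day 1 and falls back on Screening when Day 1 is unavailable. The MMRM in SAP 8.1 includes "the baseline RBANS DMI score as covariate, and a random effect for subject", and its example code has `base` as the only pre-treatment score. The imputation and ANCOVA models in SAP 8.1.1 also use only that score. No planned analysis uses the Screening DMI beside the Day 1 DMI.

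**What the plan says about noise.** SAP 3.4 reports that "the test-retest reliability is 0.80 with no practice effects using alternate versions of the test". For sample size, however, "the power analysis is based on the assumption that the standard deviation of the response variable is 16". That SD comes from the spread of single scores (14.4 to 16.5), with no reduction for baseline adjustment.

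**The concern.** With a reliability of 0.80, about 20% of the variance of a single DMI score is measurement error. A second score taken before randomization can help separate a subject's true level from that error. If it does, leaving it out keeps avoidable noise in the Week 13 difference for both doses.

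Precision matters more than usual here because SAP 8.3 tests in sequence. If 25 mg misses 0.05, 10 mg is not tested, and the secondary endpoints for each dose are gated on that dose's primary result. The trial is also meant to inform the Phase 3 dose, so interval width matters for both comparisons.

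**Working it through.** **1. The plan's own figure.** Inputs from SAP 3.4: 80 per group, difference 7.15, SD 16, two-sided 0.05.
- SE = 16 × √(2/80) = 2.53, and 7.15/2.53 = 2.83.
- Power = Φ(2.83 − 1.96) ≈ 0.807 (0.802 with the noncentral t).
- n = 2 × (1.960 + 0.842)² × 16²/7.15² = 78.6, so 79 per group.

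The stated 80% is reproduced.

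**2. Formula for the gain.** Because the Day 1 score is in the model, the residual variance of change from Day 1 equals that of the Week 13 score. Let a = corr(Screening, Day 1), b = corr(Day 1, Week 13) and c = corr(Screening, Week 13).
- Day 1 only: residual variance = SD² × (1 − b²).
- Proportional reduction from adding Screening = (c − ab)² / [(1 − a²)(1 − b²)].

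The reduction is zero when c = ab, which is serial decay: Screening then tells nothing about Week 13 beyond what Day 1 tells.

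Example with a = b = c = 0.80: (0.80 − 0.64)²/(0.36 × 0.36) = 0.0256/0.1296 = 19.8%.

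**3. Allowing for selection.** Entry on Screening DMI narrows its range. This was simulated with mean 73.4 and SD 16.5 (the amnestic MCI sample in SAP 3.4), keeping Screening ≤ 85. Only 0.80 comes from the documents, as a test-retest reliability; every b and c is an assumption.

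| a | b | c | Reduction, formula | Reduction, Screening ≤ 85 |
|---|---|---|---|---|
| 0.80 | 0.80 | 0.80 | 19.8% | 16% |
| 0.80 | 0.80 | 0.75 | 9.3% | 7.3% |
| 0.80 | 0.80 | 0.70 | 2.8% | 2.1% |
| 0.80 | 0.80 | 0.64 | 0% | 0% |
| 0.80 | 0.70 | 0.70 | 10.7% | 8.4% |
| 0.80 | 0.70 | 0.65 | 4.4% | 3.4% |
| 0.80 | 0.70 | 0.60 | 0.9% | 0.7% |
| 0.80 | 0.60 | 0.60 | 6.3% | 4.8% |
| 0.80 | 0.50 | 0.50 | 3.7% | 2.9% |

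Applying the cut-off to Day 1 as well barely changes this (about 16% in the top row).

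**4. What the top row would mean.** Residual SD falls from 9.66 to 8.86, a variance ratio of 0.841.
- SE ratio = √0.841 = 0.917, about 8% smaller; 1/0.841 = 1.19, equivalent to about 19% more subjects.
- Detectable difference at 80% power with 80 per group: 2.802 × 9.66 × 0.158 = 4.28, against 2.802 × 8.86 × 0.158 = 3.92.
- Power at an illustrative true difference of 4 units: about 74% against 81%.
- Power at 7.15 units: 99.7% against 99.9%.

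**5. Limit of the check.** These figures treat Week 13 on its own. The SAP code fits one slope per covariate across all visits, so the realized gain in the MMRM may differ somewhat.

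**The case against.** The strongest reply is that nothing here is an error. Using the last pre-dose value as the single baseline covariate is standard, and the SAP applies it consistently. That stands: this is a question of efficiency.

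The second reply concerns size, and it also stands. The 16% requires Week 13 to correlate as strongly with Screening as with Day 1. The reliability of 0.80 is quoted beside the normative mean and SD, with no retest interval and no value for early AD. The protocol also gives a reason to expect a weaker Screening correlation. Screening may be up to 28 days before dosing, or longer for washout (Protocol 5.1 and 10.2). Memantine and other centrally active drugs must be stopped within set times before Baseline or first dose (Protocol 6.2, 6.3 and 7.7). Some subjects may therefore be tested on those drugs at Screening and off them at Day 1 and Week 13. The documents do not say how many.

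A reader might also draw three stronger conclusions that the documents do not support:
- **That the primary comparison is biased because subjects were selected on Screening DMI.** Selection precedes randomization and affects all arms alike. Eligibility is also re-checked on Day 1 after RBANS is repeated (Protocol 10.3), so Screening may not be the only selecting score.
- **That the study is underpowered without the second score.** The sample size assumes SD 16 with no baseline adjustment, so the stated power does not depend on it.
- **That the Screening score is discarded outright.** SAP 6.2 keeps it as the fallback baseline.

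**Conclusion.** The point holds as a possible loss of precision and nothing more. The primary MMRM and the models in SAP 8.1.1 leave out a pre-randomization DMI score that is already collected. Given a Screening-Day 1 correlation of 0.80 and selection on Screening DMI ≤ 85, including it would reduce Week 13 residual variance by between 0% (serial decay) and about 16% (all correlations 0.80). Intermediate cases mostly give 2-8%. The documents cannot narrow this range, and washout argues against assuming the top of it. The 19% gain in effective sample size is a ceiling, not an expectation.

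Any benefit goes to interval width and to true effects smaller than 7.15 units. The change is still worth making: it cannot bias the treatment contrast and costs almost nothing.

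**What to change.** Before unblinding:
- In SAP 8.1, text and code, add the Screening RBANS DMI as a second continuous covariate beside the Day 1 DMI. Keep change from Day 1 as the outcome.
- Add the Screening DMI to the imputation steps and the ANCOVA in SAP 8.1.1.
- State that if Day 1 is missing and Screening serves as baseline, the Screening value is entered in both places.

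Replacing the Day 1 covariate with the mean of the two scores, while keeping change from Day 1 as the outcome, would not give the same gain.

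The cost is about one degree of freedom among some 240 subjects, plus edits to the model text, the code and the missing-baseline rule. No new data, visits or subjects are needed. Separately, the DMI cut-off should be made the same in Protocol 6.2 and SAP 3.3.
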